7.7 Notifying the Sponsor

The Investigators will provide the Coordinating Center with data of all SAEs as defined per the protocol on an ongoing basis. The Coordinating Center's Medical Monitor is responsible for notifying the Sponsor and will do so simultaneously with the reporting to the clinical database. As noted above, this should be within 24 hours of site awareness of the event. The Medical Monitor will review each SAE report and will determine whether the SAE must be reported to FDA/regulatory authorities on an expedited basis. The final decision for disposition regarding reporting to the FDA/regulatory authorities rests with the Sponsor or their designee. The IND Sponsor or their designee is responsible for submitting the SAE reports to FDA/regulatory authorities. The Coordinating Center will provide the DSMC with any safety reports submitted to FDA/regulatory authorities. The Coordinating Center will maintain copies of any SAE reports submitted to FDA/regulatory authorities by the Sponsor.

The Coordinating Center will provide these expedited reports to the individual site Investigators to submit to their respective IRB. Events that are serious, related to therapy and unexpected will be reported to FDA/regulatory authorities in 15 days or, for deaths and life threatening events, in 7 days (per 21 CFR 312.32).

7.8 Notifying FDA / Regulatory Authorities and the Data and Safety Monitoring Committee

After the SAE has been reported by the Principal Investigator and assessed by the IND Sponsor, the IND Sponsor or their designee must report the event to the appropriate regulatory authorities using one of these two options:

- Standard reporting (report in the annual report). This option applies if the AE is classified as one of the following:
 1. Serious, expected, suspected adverse reaction (serious, expected and related)
 2. Serious and not a suspected adverse reaction (serious and not related)
- Expedited reporting is required. This option applies if the AE is classified serious and unexpected suspected adverse reaction (serious, unexpected and related).

The Sponsor must report an adverse event as a suspected adverse reaction (related AE) only if there is evidence to suggest a causal relationship between the test article and the adverse event, such as:

- A single occurrence of an event that is uncommon and known to be strongly associated with test article.
- One or more occurrences of an event that is not commonly associated with the test article exposure, but is otherwise uncommon in the population exposed to the test article.
- Aggregate analysis of specific serious adverse events observed in a clinical trial (such as known consequences of the underlying disease or condition under investigation or other events that commonly occur in the study population independent of the test article therapy) that indicates those events occur more frequently in the test article treatment group than in a concurrent or historical control group.
- Any findings from clinical or epidemiological studies, analysis of data pooled across multiple studies, published or unpublished scientific papers or from animal or in vitro testing that would result in a safety-related change in the protocol, informed consent, General Investigational Plan section of the IND or other aspects of the overall conduct of the trial.

7.9 Reporting SAEs to the DSMC

The Coordinating Center will provide the DSMC with safety reports submitted to FDA/regulatory authorities as well as data on all SAEs on an ongoing basis.

The Investigator will ensure the timely dissemination of all AE information, including expedited reports and DSMC safety reviews, to the IRB and IEC in accordance with applicable local regulations and guidelines.

7.10 Early Termination or Participant Discontinuation

Participants may choose to withdraw from this study for any reason at any time without penalty or prohibition from enrolling in other clinical protocols.

The Investigator may discontinue a participant from the study if warranted. The Investigator and the Sponsor may also request the withdrawal of a participant because of non-compliance (e.g., missed visits), administrative reasons or any other valid and ethical reasons.

Reasons for participant discontinuation may include, but are not limited to, the following:

- Investigator determination that it is not in the best interest of the participant to continue participation
- Intercurrent illness
- Adverse event
- Worsening condition
- Any other safety concerns

If a participant withdraws or is discontinued from the study, they should return for an exit visit. The schedule of assessments for this visit is the same as that for the final visit.

The Sponsor may terminate the study earlier than planned for any reason. In the event of early termination, the Sponsor will notify the Investigators and IRBs of the decision and will provide all relevant information.

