- To investigate long term safety and efficacy of the NT-501 implant in participants previously enrolled in the NTMT-01 and NTMT-02 protocols.
- To investigate the change in the ellipsoid zone (area of [inner/outer segment] IS/OS loss) in participants previously enrolled in the NTMT-01 and NTMT-02 protocols, as measured by en face imaging by spectral domain optical coherence tomography (SD-OCT) in study eye(s).

5 Study Design and Methods

This is a prospective, multi-center, single-masked, sham-controlled follow-up study of the 7 participants that have completed 60 months of follow up in the open label NTMT-01 study (Cohort 1) and the 66 participants who completed 24 months of follow up in the NTMT-02 study (Cohort 2). All participants will be followed for an additional 48 months. Appendix 1 presents the scheduled examinations during the extended 48 month follow up period.

In the event that the NTMT-02 study is positive, Cohort 2 participants who received sham only may be eligible for active treatment in the control/non-treated eye.

6 Study Conduct

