6.7 Masking

For participants in Cohort 2 there are different levels of masking within the study. The site staff refractionist, visual acuity examiner and photographers/imagers must remain masked to treatment assignment (NT-501 implant or sham procedure) for all visits. The Ophthalmologist, Surgeon and Clinic Coordinator will be unmasked to treatment assignment.

To ensure that the refractionist, visual acuity examiner and photographers/imagers remain masked to the randomized assignment, the Ophthalmologist, Surgeon and Clinic Coordinator are not to discuss the treatment received with the refractionist, visual acuity examiner and photographers/imagers.

All personnel in the Central Image Reading Center will be masked to whether the participant received the NT-501 implant or sham in a study eye(s).

Masking will remain as described above until all 66 participants in the NTMT-02 protocol have completed their original NTMT-02 Protocol Month 24 visit and data analysis has been completed. At that time, the Principal Investigators will be informed by the Sponsor that they

may unmask the participants. They may choose to do this at the participants' next scheduled visit or in a personalized communication to the participant. The sites will notify the Coordinating Center of the unmasking as outlined in the Manual of Procedures.

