7.4 Obligations of Investigators

The Investigator is obligated to promptly report all adverse events. When submitting adverse event information, the Investigator may not delegate to someone other than a listed study physician the responsibility for reviewing the accuracy of the contents of an adverse event report. When reporting an adverse event, the Investigator must assign a severity grade to each event and also declare an opinion on the causality of the event relative to the study test article or procedure.

For any serious adverse event, the Coordinating Center and Sponsor must be notified ***within 24 hours*** of when the Investigator first learns of the occurrence of the event. Adequate information must be collected with supporting documentation to complete the standard electronic form set.

If the participant reaches the final scheduled follow-up visit, any new adverse events, as well as follow-up information for ongoing adverse events, must be recorded. For participants who

withdraw prematurely, adverse events should be followed until 30 days after last study visit. In any case, every attempt must be made by the Investigator to follow serious adverse events that are not resolved or medically stable within 30 days of the last study visit until they become resolved or medically stable.

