Surgery to remove the device may result in pain, loss of vision or blindness in rare cases. Some of these side effects can be treated with medication either by mouth or injections in or around the eye. Some side effects may require laser or surgery on the eye to treat.

A small sample (about 0.1 mL) of the vitreous along with the device may be collected and shipped back to Neurotech for analysis.

If the participants have the NT-501 device removed, they will be invited to continue to participate in the Extension Study visits and assessments until the final Extension Study visit.

11 Investigator Requirements

This study will be conducted in accordance with Good Clinical Practice (GCP), using the guidance documents and practices offered by ICH and FDA, and in accordance with the Declaration of Helsinki. This study will also comply with the regulations 21 CFR Parts 50, 54, 56 and 312 under an IND application authorized by FDA.

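### Section 7.10 permits discontinuation from the study for outcome-related reasons and offers no visits afterwards, although Section 10 invites explanted participants to continue to the end

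*Combined protocol and SAP*

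**What the plan says.** Section 4 sets the purpose: "To investigate long term safety and efficacy of the NT-501 implant in participants previously enrolled in the NTMT-01 and NTMT-02 protocols". Section 5 plans 48 further months, with four annual visits.

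Section 7.10 states: "The Investigator may discontinue a participant from the study if warranted". An open list follows ("Reasons for participant discontinuation may include, but are not limited to, the following"), which includes intercurrent illness, adverse event, "Worsening condition" and other safety concerns. For missed visits, the investigator and sponsor may only ask that the participant be withdrawn. On what comes next, the section says: "If a participant withdraws or is discontinued from the study, they should return for an exit visit". That visit has the final-visit assessments. No later visit is described.

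On safety, Section 7.2 records adverse events up to the last study visit. Section 7.4 adds that for participants who "withdraw prematurely, adverse events should be followed until 30 days after last study visit". Serious events are followed until resolved or stable (Sections 7.2 and 7.4), and adverse events leading to discontinuation are listed and tabulated (Section 8.5).

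Section 10 (Study Risks) treats device removal differently: "If the participants have the NT-501 device removed, they will be invited to continue to participate in the Extension Study visits and assessments", up to the final visit.

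Section 6.7 says of Cohort 2: "The Ophthalmologist, Surgeon and Clinic Coordinator will be unmasked to treatment assignment". Cohort 1 is open label. Section 8 gives no rule for missing data, for discontinued participants or for the use of exit-visit data.

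**The concern.** Two of the listed reasons overlap with what the study measures. Adverse events are the safety outcome. Worsening of MacTel is what ellipsoid zone loss, microperimetry and letter loss capture. If the permission is used for these reasons, the eyes that leave are not a random subset.

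The decision may also be made with knowledge of treatment, so loss could differ between NT-501 and sham. Both cohorts are fixed by the parent studies (66 and 7 participants) and cannot be refilled.

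The protocol's own treatment of explanted participants shows that continued observation was considered feasible. Section 7.10 makes no matching offer to a participant discontinued with the device in place, who may still be exposed to CNTF.

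**Working it through.** **1. The passages side by side**

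| Situation | Scheduled visits afterwards | Source |
|---|---|---|
| Device removed | Invited to continue to the final visit | Section 10 |
| Discontinued by the investigator, device in place | Exit visit only | Section 7.10 |
| Discontinued, sham-only participant | Exit visit only | Section 7.10 |

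The first row is an invitation and the others rest on a permission, so the rows can coexist. The gap is that the invitation is tied to explantation and not to discontinuation in general.

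**2. Observation lost**

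Inputs are the visit months in Section 6.9: Cohort 2 at 36, 48, 60 and 72; Cohort 1 at 72, 84, 96 and 108. Adverse events are recorded from consent at Visit 1, nominally for 72 − 36 = 36 months (Cohort 1: 108 − 72 = 36). A participant discontinued at Visit 2 loses 72 − 48 = 24 of these months (Cohort 1: 108 − 84 = 24) and two of the four annual visits. In Cohort 1 each participant lost is 1/7 = 14% of the cohort.

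**3. Possible effect on the comparison (illustration; all rates assumed)**

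The plan has no power or event-rate figure to reproduce; Section 8.3 gives only the number eligible. The Study Summary gives 98 study eyes in 66 participants, so 98 − 66 = 32 participants have two study eyes and 66 − 32 = 34 have one.

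Let p be the true proportion of eyes with a 35% or more increase in ellipsoid zone loss, and w the share of those eyes discontinued before the visit. Assume that no non-progressing eye is lost and that exit-visit data are not used. Then

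observed proportion = p(1 − w) / [p(1 − w) + (1 − p)].

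Example for sham, p = 0.30 and w = 0.40: 0.18 / (0.18 + 0.70) = 20.5%. For implant, p = 0.15 and w = 0.40: 0.09 / (0.09 + 0.85) = 9.6%.

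The observed odds are (1 − w) times the true odds. The observed odds ratio (implant to sham) is therefore the true one times (1 − w implant)/(1 − w sham).

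| True sham / implant | Progressors lost | Observed sham / implant | Difference (points) | Odds ratio |
|---|---|---|---|---|
| 30% / 15% | none | 30.0% / 15.0% | 15.0 | 0.41 |
| 30% / 15% | 20% in both | 25.5% / 12.4% | 13.2 | 0.41 |
| 30% / 15% | 40% in both | 20.5% / 9.6% | 10.9 | 0.41 |
| 30% / 15% | 40% in sham only | 20.5% / 15.0% | 5.5 | 0.69 |
| 30% / 15% | 40% in implant only | 30.0% / 9.6% | 20.4 | 0.25 |
| 50% / 30% | none | 50.0% / 30.0% | 20.0 | 0.43 |
| 50% / 30% | 40% in both | 37.5% / 20.5% | 17.0 | 0.43 |
| 50% / 30% | 40% in sham only | 37.5% / 30.0% | 7.5 | 0.71 |
| 50% / 30% | 40% in implant only | 50.0% / 20.5% | 29.5 | 0.26 |

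Differences are taken before rounding. Equal loss understates progression in both arms but leaves the odds ratio, which the GEE model of Section 8.2 compares, unchanged. Unequal loss can bias the comparison in either direction. The table treats eyes as lost singly. In practice both eyes of a discontinued participant leave together, so it shows direction and not a forecast.

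**The case against.** Several stronger readings are tempting, and the documents do not support them.

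- **That follow-up will end in precisely those with harm or progression.** Section 7.10 is a permission, its list also holds reasons unrelated to outcome, and nothing requires discontinuation after an event.
- **That Sections 7.10 and 10 contradict each other.** An invitation after explantation and a discretionary power to discontinue are compatible.
- **That discontinuation for an adverse event hides the event.** The triggering event is recorded and tabulated, serious events are followed to resolution or stability, and a medical monitor and an independent committee review safety (Section 7.11). Only later events are missed.
- **That this is a pure observation study in which every discontinued participant keeps an implant.** Sham-only participants have none, and Section 5 says they may become eligible for active treatment. That the device stays in is inferred from silence in Section 7.10; Section 7.6 considers removal and termination together in the case of pregnancy.

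Two further points have weight. The exit visit includes visual acuity and SD-OCT, so worsening that prompted discontinuation would normally be measured, and the illustration above gives that measurement no weight. Also, Section 6.7 names the ophthalmologist, surgeon and coordinator, not the investigator; that the person deciding is unmasked is the natural reading, but not a stated fact.

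What remains is that the exit measurement has no stated place in the analysis, and that 30 days of follow-up does not replace up to two further years of visits after Visit 2. The mixed model in Section 8.2 names a random effect for the correlation between eyes and a treatment effect, with no visit term, so earlier data need not inform a missing late value.

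**Conclusion.** The concern holds in a limited form. Section 7.10 allows loss that depends on outcome, and possibly on arm, in a study whose purpose is long-term safety and efficacy. It offers no continued visits to those affected. The remaining annual efficacy data and later new events are lost.

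The size of any bias is unknown, because the documents give no event, progression or discontinuation rates. Under the assumed rates, a true 15.0-point difference could be observed as anything from 5.5 to 20.4 points, and a true 20.0-point difference as 7.5 to 29.5. These ranges assume that 40% of progressing eyes are lost in one arm only and that exit data are ignored. If loss is proportionally equal, the odds ratio is unaffected and only the proportions are understated. The change is worth making because it is cheap, not because bias has been shown.

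**What to change.** - Reconcile Section 7.10 with Section 10. State that a participant discontinued by the investigator or sponsor, for any reason other than withdrawn consent, is invited to the remaining annual visits through Month 72 (Cohort 2) or Month 108 (Cohort 1), whatever the device status. Care decisions stay with the investigator. Deleting items from the list would not help: the list is open and the general discretion would remain.
- Where visits stop but consent and authorization remain, collect adverse events, serious adverse events and implant status from available records at the scheduled time points.
- Record the reason for each discontinuation and the role of the person who decided, and tabulate both by arm.
- In Section 8.2, state how exit-visit data enter the analysis: actual time since surgery for continuous outcomes, and whether a threshold met at exit counts at later visits for dichotomous ones.
- Add a missing-not-at-random sensitivity analysis in which assumptions about unobserved outcomes vary separately by arm.

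The cost is some additional annual visits, all on the existing schedule, together with record requests and alignment of the consent form. Record collection depends on the authorization described in Section 11.7, so it needs consent wording as well as a protocol edit.

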7.11 Safety Monitoring

A medical monitor will be assigned to review safety information throughout the study. An independent Data and Safety Monitoring Committee (DSMC) will operate according to the DSMC Charter that will specify operations, roles and responsibilities and communication with the Sponsor.

8 Statistical Considerations

All analyses will be conducted separately for each Cohort.

8.1 Efficacy Outcomes

Cohort 1

Efficacy outcomes to investigate the efficacy of CNTF produced by NT-501 include (all changes relative to NTMT-01 baseline measurements):

- Change in the ellipsoid zone (area of IS/OS loss) from baseline to Months 72, 84, 96 and 108.
- Change in retinal sensitivity (dB) as measured by microperimetry from baseline to Months 72, 84, 96 and 108.
- Proportion of study eyes with a 35% or more increase from baseline in the ellipsoid zone (area of IS/OS loss) at Months 72, 84, 96 and 108.
- Change in BCVA from baseline to 72, 84, 96 and 108.

- Proportion of study eyes with 15 or more letter loss from baseline in BCVA at 72, 84, 96 and 108.
- Proportion of study eyes with 10 or more letter loss from baseline in BCVA at 72, 84, 96 and 108.

Cohort 2

The outcomes to investigate long term efficacy of CNTF or NT-501 include (all change relative to NTMT-02 baseline measurements):

- Change in ellipsoid zone (area of IS/OS loss) from baseline to Months 36, 48, 60 and 72.
- Change in retinal sensitivity (dB) as measured by microperimetry from baseline to Months 36, 48, 60 and 72.
- Proportion of study eyes with a 35% or more increase from baseline in the ellipsoid zone (area of IS/OS loss) at Months 36, 48, 60 and 72.
- Change in BCVA from baseline to Months 36, 48, 60 and 72.
- Proportion of study eyes with 15 or more letter loss from baseline in BCVA at Months 36, 48, 60 and 72.
- Proportion of study eyes with 10 or more letter loss from baseline in BCVA at Months 36, 48, 60 and 72.
- Change in reading speed from baseline to Months 36, 48, 60 and 72.

8.2 Analyses in Support of the Efficacy Outcomes

Cohort 1

For continuous measures mean, median and distribution of change from baseline in BCVA, and enlargement of inner/outer segment discontinuity as measured by SD-OCT will be computed separately for study eyes and fellow eyes. For dichotomous outcomes proportions along with 95% confidence intervals will be computed separately for study eyes and fellow eyes.

Cohort 2

Continuous efficacy measures will be assessed using mixed effects models with an overall Type I error rate of 0.05 (no adjustments of the type I error rate will be made). Due to clustered data (data from two eyes for a percentage of the participants), the variability associated with the estimates of effect (mean difference) from a fixed effects model is likely to be biased, leading to

incorrect test statistics and confidence intervals. For example, if the correlation from paired eyes is ignored, the standard error for the treatment effect is likely to be overestimated when paired eyes from the same participant are in different treatment groups. For this reason, the unpaired t-test for the comparison of means between two treatment groups is not appropriate as it assumes that observations from the same cluster are independent. The appropriate statistical analysis of clustered data should take such correlation into consideration which can be accomplished for continuous outcome measures using a mixed effects model. The mixed effects model will incorporate both random (accounting for the correlation between eyes) and fixed effects (treatment) into the model and will be estimated with accompanying 95% confidence intervals and compared between treatment groups. For dichotomous outcomes, logistic regression incorporating the generalized estimation equation (GEE) methodology with accompanying 95% confidence intervals will be performed to determine if there are significant differences in the odds between the two treatment groups.

The efficacy analyses will be repeated to investigate the strength of potential predictors using multivariable mixed effects models or multiple logistic regression models. Examples of potential predictors include the following: baseline visual acuity, clinical site, participant's age at enrollment and gender.

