Participant visits will occur at Months 72, 84, 96 and 108 (+/- 1 month) following the date of the surgical procedure for NTMT-01.

Cohort 2 - Prospective, multi-center, single-masked sham-controlled study. All participants will have been enrolled (undergone a NT-501 implant and/or sham procedure) in the *A Phase 2 Multicenter Randomized Clinical Trial of Ciliary Neurotrophic Factor (CNTF) for Macular Telangiectasia Type 2 (MacTel NTMT-02)* protocol and have agreed to continue in this follow-up study.

In the event that the NTMT-02 study is positive, Cohort 2 participants who received sham only may be eligible for active treatment in the control/non-treated eye.

Participant visits will occur at Months 36, 48, 60 and 72 (+/- 1 month) following the date of the surgical procedure for NTMT-02.

Sample Size:

Cohort 1 - 7 participants (7 study eyes) – previously enrolled in NTMT-01 protocol

Cohort 2 – 66 participants (98 study eyes) – previously enrolled in NTMT-02 protocol

Diagnosis and Key Eligibility Criteria: Previously enrolled in NTMT-01 or NTMT-02 protocols

Investigational Product: NT-501 implant

Duration of Treatment:

Cohort 1 - Visits to continue until Month 108 from date of study procedure, with annual analyses at Months 72, 84, 96, and 108.

Cohort 2 - Visits to continue until Month 72 from date of study procedure, with annual analyses at Months 36, 48, 60, and 72.

Number of Centers: 8 sites in the United States and 3 sites in Australia

Study Outcomes:

Cohort 1: The following efficacy outcomes as outlined in the NTMT-01 Protocol will continue to be analyzed to investigate the efficacy of Ciliary Neurotrophic Factor (CNTF) produced by NT-501 (all changes relative to NTMT-01 baseline measurements):

- Change in the ellipsoid zone (area of IS/OS loss) from baseline to Months 72, 84, 96 and 108.
- Change in retinal sensitivity (dB) as measured by microperimetry from baseline to Months 72, 84, 96 and 108.
- Proportion of study eyes with a 35% or more increase from baseline in the ellipsoid zone (area of IS/OS loss) at Months 72, 84, 96 and 108.
- Change in best corrected visual acuity (BCVA) from baseline to Months 72, 84, 96 and 108.
- Proportion of study eyes with 15 or more letter loss from baseline in BCVA at Months 72, 84, 96 and 108.
- Proportion of study eyes with 10 or more letter loss from baseline in BCVA at Months 72, 84, 96 and 108.

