Cohort 2: The following efficacy outcomes as outlined in the NTMT-02 Protocol will continue to be analyzed to investigate the efficacy of Ciliary Neurotrophic Factor (CNTF) produced by NT-501 (all changes relative to NTMT-02 baseline measurements):

- Change in the ellipsoid zone (area of IS/OS loss) from baseline to Months 36, 48, 60 and 72.
- Change in retinal sensitivity (dB) as measured by microperimetry from baseline to Months 36, 48, 60 and 72.
- Proportion of study eyes with a 35% or more increase from baseline in the ellipsoid zone (area of IS/OS loss) at Months 36, 48, 60 and 72.
- Change in BCVA from baseline to Months 36, 48, 60 and 72.
- Proportion of study eyes with 15 or more letter loss from baseline in BCVA at Months 36, 48, 60 and 72.
- Proportion of study eyes with 10 or more letter loss from baseline in BCVA at Months 36, 48, 60 and 72.
- Change in reading speed from baseline to Months 36, 48, 60 and 72.

Assessment/Examination Schedule

	VISIT 1 (+/- 1 month)	VISIT 2 (+/- 1 month)	VISIT 3 (+/- 1 month)	VISIT 4 (+/- 1 month)
VISITS ARE SCHEDULED FROM THE DATE OF THE NTMT-01 OR NTMT-02 SURGERY				
GENERAL ASSESSMENTS				
NTMT-01/02 Extension Study Consent	X			
Review Eligibility Criteria	X			
Review Demographics and Participant Contact Information	X			
Update Medical & Ophthalmic History from NTMT-01 and NTMT-02 -This will include AEs collected during NTMT-01 and NTMT-02 and up to Visit 1 of the Extension Study as applicable. Any events between the last NTMT-01 or NTMT-02 visit will be recorded here.	X			
AE Assessment – starting from date of NTMT-01/02E Consent		X	X	X
Concomitant Medications – continue from NTMT-01 and NTMT-02	X	X	X	X
Reading Speed* *Completed for NTMT-02 (Cohort 2) participants only	X*	X*	X*	X*
VISUAL SYSTEM EXAMS: UN-DILATED				
Manifest Refraction	X	X	X	X
Best Corrected Visual Acuity	X	X	X	X
Applanation Tonometry (Goldmann applanation tonometer)	X	X	X	X
Microperimetry	X	X	X	X
VISUAL SYSTEM EXAMS: DILATED				
Slit lamp Biomicroscopy	X	X	X	X
Dilated Fundus Examination	X	X	X	X
Implant Site Clinical Examination	X	X	X	X
SD-OCT	X	X	X	X
Fundus Autofluorescence Imaging	X	X	X	X
Digital Color Fundus Photographs	X	X	X	X
AOSLO (for participants enrolled at NTMT-02 baseline) Requires separate consent at AOSLO Center	X**	X**	X**	X**

Table of Contents

1	Précis.....	1
2	Background and Rationale	2
3	Scientific Rationale.....	5
	3.1 Encapsulated Cell Technology (ECT)	5
4	Study Objectives	6

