3.1 Encapsulated Cell Technology (ECT)

This study is designed to provide long term observation of the ongoing effect of CNTF as delivered continuously via the NT-501 implant in patients with MacTel type 2. MacTel type 2 is a slowly progressive condition which may take many years to develop clinical symptoms and signs.

The Phase II NTMT-02 trial was limited to 24 months of controlled observation. While it is anticipated that two years of controlled observation should be sufficient to determine efficacy, it is possible that a longer period is necessary to observe a meaningful separation between the groups. This extension study provides the opportunity for that continued observation.

Previous experience with the NT-501 implant in studies of participants with geographic atrophy or retinitis pigmentosa suggests that the implant is capable of delivering detectable CNTF for up to 66 months. Output of CNTF from explanted devices, along with vitreous levels of CNTF, is consistent with the histologic findings at these various time points; the cells remain healthy and productive within the membranes (capsules), and continue to produce and deliver CNTF. These data support the hypothesis that NT-501 will continue to provide similar levels of CNTF to the

study eyes during this prolonged follow up period. Mean duration of implantations together with explant and vitreous CNTF levels are shown in Table 2.

Table 2: Ex vivo production rates and vitreous CNTF concentrations at the time of NT-501 explantation

Implant Duration	Explant (ng/ day)	#	Vitreous (pg/mL)	#
6 months	1.54 ± 0.54	(5)	58 ± 0	(1)
12-13 months	2.09 ± 0.59	(11)	64 ± 0	(2)
18-20 months	1.78 ± 0.86	(7)	57 ± 0	(1)
24 months	1.08 ± 0.48	(11)	46 ± 0	(1)
30-33 months	1.10 ± 0.73	(6)	17 ± 0	(1)
45 months	1.25 ± 0.00	(1)	55 ± 0	(1)
54 months	0.70 ± 0.04	(2)	---	
66 months	1.16 ± 0.00	(1)	36 ± 0	(1)

The Phase I NTMT-01 trial designed to assess the safety and tolerability of the NT-501 implant in patients diagnosed with MacTel type 2 has completed enrollment (N=7) and follow-up continues. No serious adverse reactions have been reported to date. Preliminary data confirm that the progression of visual impairment is slow in MacTel type 2. This is consistent with the findings of Heeren et al (2015) who suggested that patients with MacTel type 2 require prolonged follow up for appropriate evaluation of functional loss.

4 Study Objectives

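### Section 8.2 claims an overall Type I error rate of 0.05 for Cohort 2's four unranked continuous outcomes with no adjustment, and nothing in the plan makes that rate true

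*Combined protocol and SAP*

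**What the plan says.** All places are in the combined protocol and SAP.

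- **Section 8.2, Cohort 2.** Continuous efficacy measures are assessed with "mixed effects models with an overall Type I error rate of 0.05 (no adjustments of the type I error rate will be made". The rate and the absence of adjustment stand in one sentence. Later in the section, the mixed-model effects "will be estimated with accompanying 95% confidence intervals and compared between treatment groups".
- **Section 8.1, Cohort 2** (repeated in Section 6.1.2). Four continuous outcomes are listed: change in ellipsoid zone area, in retinal sensitivity, in BCVA and in reading speed. Each is given at four visits, for example "Change in reading speed from baseline to Months 36, 48, 60 and 72". None is ranked.
- **Study Summary, Duration of Treatment.** Cohort 2 is followed "with annual analyses at Months 36, 48, 60, and 72".
- **Study Summary, Study Outcomes.** The "efficacy outcomes as outlined in the NTMT-02 Protocol will continue to be analyzed"; no order among them is given.
- **Section 4.** The second objective begins "To investigate the change in the ellipsoid zone". It does not call that outcome primary.
- **Section 8.6.** A quality-assurance bullet mentions a primary outcome measure and secondary ones without identifying either.
- **Section 3.1.** After saying that two years should be enough to determine efficacy, the rationale adds that "it is possible that a longer period is necessary to observe a meaningful separation between the groups".

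**The concern.** In a plan with several outcomes, an overall Type I error rate is normally read as the chance of at least one false positive across them. Four separate tests at 0.05 do not have that property. It could be had without splitting the level if the plan named a single test, fixed an order of testing, or required every outcome to be significant before claiming an effect. None of these appears.

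What is at stake is how a between-group result would be read. Section 3.1 gives possible later separation of the groups as one reason for the extension. If one of the four outcomes came out at p<0.05, a report could cite Section 8.2 and present it as found under 5% overall control. The estimates and their 95% confidence intervals are not affected.

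**Working it through.** **Inputs from the document**

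- Stated overall level 0.05, with no adjustment (Section 8.2).
- Number of continuous outcomes in Cohort 2: 4 (Section 8.1).
- Visits per outcome: 4 (Section 8.1; Study Summary).

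**Assumptions, because the document is silent**

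- Two-sided tests, in line with the 95% confidence intervals.
- One test per outcome, the smallest count that covers the list.
- No true effect on any outcome.
- Jointly normal test statistics with a common correlation r.

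**Step 1: the plan's own figure.** A single two-sided test with |z| > 1.96 has an error rate of 0.0500. The stated 0.05 therefore reproduces for one test.

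**Step 2: four independent tests.** 1 − (1 − 0.05)^4 = 1 − 0.95^4 = 1 − 0.81450625 = 0.1855, or 18.5%.

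**Step 3: four correlated tests.** With a common normal factor u, standard normal density φ and distribution function Φ,

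P(at least one |z| > 1.96) = 1 − ∫ φ(u) · [Φ((1.96 − √r·u)/√(1−r)) − Φ((−1.96 − √r·u)/√(1−r))]^4 du.

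| Assumed r | At least one p<0.05 among four |
|---|---|
| 0 | 18.5% |
| 0.2 | 18.0% |
| 0.5 | 15.6% |
| 0.7 | 13.0% |
| 0.8 | 11.4% |
| 0.9 | 9.4% |
| 0.99 | 6.3% |

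A simulation with 400,000 draws gave 18.5%, 15.6% and 9.3% at r = 0, 0.5 and 0.9.

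**Step 4: sensitivity to sidedness.** One-sided 0.05 tests give 18.5%, 14.4% and 8.8% at r = 0, 0.5 and 0.9, so the conclusion does not depend on this assumption.

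**Step 5: comparison.** Between r = 0.9 and r = 0, the rate is 9.4/5 = 1.9 to 18.5/5 = 3.7 times the stated one. It comes down to 5% only when r reaches 1, that is, when the four tests are in effect one.

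The three dichotomous outcomes and the repeated models with predictors are not counted, because the error-rate sentence covers only the continuous measures.

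**The case against.** The strongest reply is that the sentence discloses what it does. A reader who sees 0.05 also sees that nothing is adjusted, and may take 0.05 as the nominal level of each model. This is a Phase 2 follow-up study with a carried-over sample, no power calculation and objectives worded as investigation. No success criterion uses the extension's p-values, and possible active treatment of sham participants depends on NTMT-02 being positive. All of this stands, and it limits the consequence. It does not rescue the word *overall*, which says something other than a nominal level per model.

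A second reply is that a hierarchy exists elsewhere: in the NTMT-02 protocol, or implied by the separate ellipsoid zone objective. The Study Summary carries over outcomes and states no ranking. The NTMT-02 protocol is not among the documents, so a ranking there cannot be assumed. Section 4 does not tie the error rate to the ellipsoid zone, and no lead visit is named.

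A reader might infer more than the documents support:

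- **That unadjusted testing is itself the fault.** It is disclosed and acceptable here.
- **That only a single test or a test sequence could reconcile the two statements.** An all-outcomes-must-be-significant rule would also keep the rate at or below 0.05; the plan simply states none of the three.
- **That the relevant count is 4 × 4 = 16 tests.** With equal correlation this would give 37.4% at 0.5 and 14.6% at 0.9. The annual analyses make separate testing possible, but Section 8.2 does not say that each visit is tested, so these figures cannot carry the point.
- **That later separation is the sole reason for the extension.** Section 3.1 also gives long-term observation of the ongoing effect, and expects two years to suffice for efficacy.

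**Conclusion.** The point holds as an error in a stated property. The overall rate in Section 8.2 does not follow from the analysis described there and in Section 8.1. On the smallest reasonable count it is 18.5% under independence, 15.6% at r = 0.5 and 9.4% at r = 0.9, against a stated 5%. These sizes rest on assumed correlations, two-sided tests, one test per outcome and no true effect. The direction does not rest on the correlation chosen: every value of r in the table gives more than 5%. Separate testing of the annual visits would raise the rate further. The defect should be corrected, but it does not invalidate the estimates, the confidence intervals or any decision in the plan.

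**What to change.** In Section 8.2, Cohort 2, keep the choice of mixed effects models for continuous measures and replace the error-rate clause and its bracket with:

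*Each comparison uses a nominal two-sided 0.05 level; no adjustment is made, and the overall Type I error rate across outcomes and visits is not controlled.*

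The cost is one sentence. No data, analysis or power is affected. The downside is that the stated error control becomes less favourable.

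If the sponsor prefers to keep an overall 0.05 claim, the plan must contain a rule that delivers it: one lead outcome at one lead visit, a stated test sequence, or a requirement that all outcomes be significant. That rule must have been chosen before the NTMT-02 Month 24 or later results were known. Timing matters because Section 6.7 lets the Principal Investigators unmask participants once all 66 have "completed their original NTMT-02 Protocol Month 24 visit and data analysis has been completed", so those results can be available while the extension is running. A lead outcome chosen after that should not be presented as restoring 5% control.
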